7.4. Statistical Analysis

The statistical analysis will follow the procedure outlined in ISO 80601-2-56:2017 section 201.102.

7.4.1. Exclusion

Data from the following participants will be excluded from data analysis:

- Any subject administered antipyretic medications during study participation
- Any subject who does not complete at least one full round of measurements.
- Any subject whose data suggests a defective device or sensor.
- Any subject whose data suggests existence of external conditions that interfere with Rad-GT or reference measurements.

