6.5.2. Consenting and Screening

Per FDA Guidance “IRB Waiver or Alteration of Informed Consent for Clinical Investigations Involving No More than Minimal Risk to Human Subjects” issued on January 2017, waiver of documentation of informed consent for certain FDA-regulated minimal risk clinical investigations will facilitate investigators’ ability to conduct studies that may contribute substantially to the development of products to diagnose or treat diseases or conditions, or address unmet medical needs. The IRB can waive the requirements to document informed consent when the IRB finds that:

- The clinical investigation involves no more than minimal risk (as defined in 21 CFR 50.3(k) or 56.102(i)) to the subjects;
- The waiver or alteration will not adversely affect the rights and welfare of the subjects;
- The clinical investigation could not practicably be carried out without the waiver or alteration;
- Whenever appropriate, the subjects will be provided with additional pertinent information after participation

This study meets all the criteria listed by the FDA above and involves no more than minimal risk to the study participants because (1) the device under study is non-contact and (2) the clinical data to be obtained includes data collected for routine clinical use. The waiver is not expected to adversely affect the rights and welfare of the study participants because the study involves no-touch procedures and all data to be collected will be protected as outlined in the data collection and storage procedures. The clinical investigation could not practicably be carried out without the waiver due to the timing of the clinical assessment and immediate treatment of febrile conditions with antipyretics for children and adolescents in the Emergency Department.

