After a caregiver/patient or their parent/LAR checks into the Emergency Department, a nurse or trained study investigator will approach them, and ask if they would like to participate in a short study looking at fever. If the patient or their parent/LAR is interested, an informational sheet outlining the study will be provided to them. This Study Information Sheet will be available in English and Spanish, the two most common languages in Orange County, California. The information sheet will be provided prior to the start of the study to inform the patient and/or their parent/LAR about the study and what data will be collected. Content on the information sheet will include: (1) research purpose and procedures, (2) risks, (3) benefits, (4) confidentiality, (5) whom (and how) to contact study personnel, (6) the voluntary nature of human research and the ability to withdraw participation, and (7) reporting of significant new findings. If the participant or their parent/LAR verbally agrees, they will be considered enrolled in the study. Verbal consent from the study investigator will be collected after review of the information sheet. Reasonable and appropriate protections will be implemented so that risks related to invasion of privacy and breach of confidentiality is no greater than minimal. After having the opportunity to review the information sheet, study participants or their parent/LAR will have the opportunity to decline participation in the study. After participants have verbally consented, they will be entered into the study system and study procedures outlined in the protocol will proceed.

HIPAA Waiver for Participant Screening

The screening of participants will require the investigators to access personal health information to identify prospective participants without HIPAA authorization. The participants’ rights and welfare will not be adversely affected by waiving HIPAA authorization. This protected health information will not be inappropriately reused or disclosed to any other person or entity. To further safeguard all protected health information, the data will not be labeled with any personal identifying information. Also, the data will not be stored with any protected health information identifiers.

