6.5.3. Data Collection Procedure

6.5.3.1. Data collected by the Rad-G with Temperature is not intended to be used for clinical decisions, and research personnel should continue to use standard of care procedures for monitoring participants.

6.5.3.2. Study duration will be approximately 15 to 30 minutes.

6.5.3.6. Record start and end time of data collection procedures on the CRF.

6.5.3.7. Take the screening temperature measurement using the same thermometer to be used for the reference measurements, immediately before beginning the study measurements. The subject should be withdrawn from the study if they do not meet the criteria for temperature [REDACTED]

Reference Measurements

Multiple reference measurements may be obtained.

6.5.3.12. The three measurements need to be taken in quick succession of each other, with approximately 3 seconds between each measurement

6.5.3.13. Be sure to keep the Rad-G device steady during the measurement.

6.5.3.15. In the validation phase, [REDACTED] measurements will be obtained per subject.

6.5.3.16. Data from the Rad-G with Temperature device will be downloaded using Masimo [REDACTED] software on the data collection laptop at the end of each day. Reference data [REDACTED] will be downloaded to the data collection laptop using a USB flash drive.

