8.3. Case Report Forms

The site shall capture study data in case report forms (CRFs) for each participant enrolled, to be provided to the sponsor. CRFs may be in paper or electronic format through electronic data capture (EDC) software. Masimo shall ensure that systems used for electronic CRFs are compliant with the requirements of 21 CFR Part 11 and ISO / IEC 27001 Certification. The CRFs will be completed and signed by the principal investigator or delegate. This also applies to those participants who fail to complete the study. If a participant withdraws from the study, the reason must be noted on the CRF. Case report forms are to be completed on an ongoing basis. CRF entries and corrections will only be performed by study site staff, authorized by the investigator. For paper CRFs, entries and corrections to the CRF will be made following Good Documentation Practices.

The CRF may include the following information, including but not limited to: inclusion / exclusion criteria, whether participant consent was obtained before start of study, demographic information, device readings, and if occurrence of any adverse event, protocol deviation, and device deficiencies, etc. The CRFs will be signed by the PI or delegate to attest that the data are complete and accurate.

CRF entries will be checked by the study monitor and any errors or inconsistencies will be queried to the site on an ongoing basis. Any changes made within an electronic CRF will be tracked by audit trail. Any changes on a paper CRF will be made directly on the CRF and will be initialed and dated by the person making the change. Query resolution will be assessed and confirmed by study monitor during site visit.

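### Does the antipyretic exclusion in 7.4.1 need rewriting because it drops the whole subject and does not say when participation starts and ends?

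*Combined protocol and SAP*

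**What the plan says.** Section 7.4.1 (Exclusion) opens with "Data from the following participants will be excluded from data analysis" and lists four grounds. The first is "Any subject administered antipyretic medications during study participation". The second is "Any subject who does not complete at least one full round of measurements". The other two cover a defective device or sensor and outside interference with either instrument. All four remove the subject, not single readings.

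Three other sections bear on when participation starts and ends:

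- Section 6.5.2 fixes enrolment: "If the participant or their parent/LAR verbally agrees, they will be considered enrolled in the study". Entry into the study system and the procedures follow.
- Section 6.5.3.2 gives the length: "Study duration will be approximately 15 to 30 minutes".
- Section 6.5.3.6 instructs staff: "Record start and end time of data collection procedures on the CRF".

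Section 6.5.2 also supports the consent waiver by pointing to "immediate treatment of febrile conditions with antipyretics for children and adolescents in the Emergency Department", so doses close to the measurements are to be expected. Section 8.3 describes the CRF contents in open-ended terms, including "demographic information, device readings, and if occurrence of any adverse event, protocol deviation, and device deficiencies, etc". Section 7.4 leaves the analysis procedure to ISO 80601-2-56:2017, section 201.102.

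**The concern.** A dose cannot alter a paired reading that has already been taken. Removing such readings therefore looks like discarding valid data because of a later event. The next item in the list strengthens that impression, since it asks only for one complete round.

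The window also looks open. Take a subject who agrees, receives an antipyretic, and is then measured. That subject is out if participation starts at agreement and in if it starts with data collection. The named CRF items include no dose and no dose time. Two analysts might then build different validation sets from the same records. Because the protocol itself expects prompt treatment, the situation is not far-fetched. At stake would be the size and reproducibility of the set from which the accuracy result is computed.

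**Working it through.** The question is mainly one of wording, so the relevant provisions are set side by side first. The arithmetic after that is for scale only.

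**1. Do the first two exclusions conflict?** The second removes a subject with less than one complete round. That makes a complete round necessary for inclusion. It does not make it sufficient. A subject with many rounds and a faulty sensor is also removed whole. The grounds are independent and do not contradict each other.

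**2. How wide is the ambiguity?** There are two candidate windows: (a) verbal agreement to the end of the visit, and (b) recorded start to recorded end of data collection. They can differ for a dose between agreement and the first reading. They can also differ for a dose after the last reading but before the visit closes. Section 6.5.2 treats the subject as enrolled from agreement, so (a) is the ordinary reading. Nothing in the documents suggests that either gap is long or common.

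**3. What must be recorded?** The rule as written needs a yes or no: was a dose given during the visit? A dose time becomes essential only if single rounds are to be kept or dropped. The CRF list in 8.3 is expressly not exhaustive, so a missing item there shows nothing.

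**4. How much data could be lost?** The documents give no dosing rate, so the total cannot be computed. What can be computed is how many dosed subjects would already have a complete round. Assume the dose time is uniform over a visit of length T and the first round is complete at time t. The share is 1 − t/T. T comes from 6.5.3.2; t and the uniform dose time are assumptions.

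| T (min) | t = 5 min | t = 10 min |
|---|---|---|
| 15 | 1 − 5/15 = 67% | 1 − 10/15 = 33% |
| 30 | 1 − 5/30 = 83% | 1 − 10/30 = 67% |

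These are shares of dosed subjects, not of the trial, and they depend on the assumed t.

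**5. Can the loss be absorbed?** Section 7.3 sets a minimum of 32 febrile validation patients. It takes this from the cited standard and shows no formula inputs, so the figure cannot be reproduced; it is not in dispute here. To keep 32 after a proportion d is excluded, enrol 32/(1 − d), rounded up:

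| Assumed d | 32/(1 − d) | Enrol |
|---|---|---|
| 5% | 33.7 | 34 |
| 10% | 35.6 | 36 |
| 20% | 40.0 | 40 |
| 30% | 45.7 | 46 |
| 50% | 64.0 | 64 |

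Section 6.1 caps enrolment at 250. If all 250 places went to validation, the loss could reach 1 − 32/250 = 87.2% before the count fell below 32. The cap also covers the calibration group and the split is not visible, so the true margin is smaller by an unknown amount.

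**6. What cannot be seen?** Steps 6.5.3.3 to 6.5.3.5, 6.5.3.8 to 6.5.3.11 and 6.5.3.14 are not shown, and the number of validation measurements per subject in 6.5.3.15 is redacted. The round structure, and any instruction on antipyretic timing, could well sit there.

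**The case for a change.** The best case for a change does not need a contradiction between the two exclusions. It rests on the first alone: for rounds finished before the dose, the rule has no measurement reason to remove them. The link between participation and a recorded time is missing from the visible text. Spare enrolment replaces lost subjects, but it does not settle who belongs in the set. The remedy would be cheap: one reworded line and one CRF field.

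Some of this stands. The rule does ignore timing, and a sentence naming the window would remove a small doubt. The proposed remedy is less clearly a gain. Keeping earlier rounds means matching dose times to round times, and subjects would contribute unequal numbers of rounds. That may not fit the redacted per-subject measurement count or the ISO procedure, which cannot be checked from these documents. A sponsor may reasonably prefer a rule that is objective, fixed in advance and simple to apply.

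Nor has an effect on the result been shown. For the exclusion to bias the accuracy estimate, the difference between device and reference would have to be systematically different in dosed subjects, before their dose, from that in the others. The documents offer no evidence on this.

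**Conclusion.** No change to the plan follows. Whole-subject exclusion is a conservative, pre-specified choice, and the alternative trades some retained data for added complexity and an unverified fit with the ISO method. The undefined window is a missing detail that an analyst would fill sensibly by counting from verbal agreement to the recorded end time. Withheld procedure steps may already fill it.

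The total loss cannot be sized. The 33% to 83% range applies only to dosed subjects and rests on assumed timings. The 34 to 64 enrolled needed to keep 32 rests on assumed exclusion rates of 5% to 50%. The conclusion assumes that the calibration group leaves room for replacement under the cap of 250, and that dosing is not tied to device error. If the sponsor wishes, a note in the analysis file can name the window and confirm that the whole subject is removed. Nothing here bears on whether or when patients are treated.

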7. STATISTICAL DESIGN AND ANALYSIS

7.1. Acceptance Criteria

7.3. Sample Size

The [REDACTED] minimum of 32 febrile patients for the validation phase per ISO 80601-2-56:2017, section 201.102.

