8.4. Data Transfer and Storage

Original paper CRFs will be stored in a secure location at the site. Copy of the original paper CRFs may be scanned and sent to sponsor. If using electronic CRFs, the site staff will be assigned unique usernames and passwords for data security. Final copies of the electronic CRFs in EDC are stored on a secure server.

Only authorized sponsor personnel will have access to study data, and will move it to a secure and backed-up drive at Masimo.

CRFs will be checked for completeness and if there are inconsistent or missing data points, queries will be generated. If delegated study staff are to correct the paper CRF, they shall follow GDP practices to strike through old entry, add in new entry, and initial and date it, and provide the corrected information to sponsor. Corrections made to electronic CRFs will be tracked by audit trail and require PI or delegate sign-off.

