Note: Anticipated serious adverse device effect (ASADE) is an effect which by its nature, incidence, severity or outcome has been identified in the risk assessment.

- **device deficiency**: inadequacy of a medical device with respect to its identity, quality, durability, reliability, usability, safety or performance

Note 1: Device deficiencies include malfunctions, use errors, and inadequacy in the information supplied by the manufacturer including labelling.

Note 2: This definition includes device deficiencies related to the investigational medical device or the comparator.

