14.4. Device Deficiencies Reporting

All Masimo device related deficiencies should be reported to the Sponsor and must be recorded in the CRF in a timely manner. When a Masimo device deficiency is observed, every effort should be made to return the device and its packaging to the Sponsor in a timely manner.

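### Section 7.4.1 lets whole subjects be dropped because their data suggest a fault or interference, without evidence independent of the Rad-G-minus-reference difference, so it permits exclusion by size of error

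*Combined protocol and SAP*

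**What the plan says.** Section 7.4.1 of the combined protocol and SAP lists four grounds for excluding a participant's data from analysis. Two are facts that can be checked without looking at the error: an antipyretic was given during participation, or not even one full round of measurements was completed. The other two rest on what the data look like: "Any subject whose data suggests a defective device or sensor" and "Any subject whose data suggests existence of external conditions that interfere with Rad-GT or reference measurements". The unit removed is the whole participant, and the list shows no redaction mark.

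The synopsis (section 1) gives the validation endpoint as accuracy of the Rad-G against reference temperatures. Section 7.3 sets a "minimum of 32 febrile patients for the validation phase". Section 7.4 hands the analysis to an ISO procedure that is not reproduced.

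On records that could support an exclusion, section 14.4 says: "All Masimo device related deficiencies should be reported to the Sponsor and must be recorded in the CRF in a timely manner". Section 8.3 names device deficiencies among the items that a CRF may contain, and section 14.1 says of the term: "This definition includes device deficiencies related to the investigational medical device or the comparator".

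**The concern.** In an agreement study, a large Rad-G-minus-reference difference is the outcome. It is also the most obvious thing in a subject's data that could suggest a faulty device or outside interference. A rule triggered by the data, with no other evidence required, therefore leaves room to select on the outcome.

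If the subjects removed are those with the largest absolute differences, the spread of the differences is understated and the device looks more precise than it is. The effect on mean bias can go either way, depending on which tail loses subjects. Removing a reading with a verified fault in either instrument is legitimate. The difficulty is that, from the visible text, a reader of the results could not tell a verified fault from a merely large error. Section 17 says that the validation results will be made public, so this matters beyond the sponsor.

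**Working it through.** **Does any other visible text close the gap?**

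- *Device deficiencies (14.1, 14.4, 8.3).* Deficiencies of Masimo devices must be recorded. Those of the reference thermometer may be recorded, since 8.3 allows device deficiencies in the CRF and 14.1 includes the comparator in that term, but the visible text does not require it. Section 7.4.1 makes exclusion depend on neither record.
- *Interfering conditions.* No visible section calls for them to be noted when they occur.
- *Timing of CRF entries.* Section 8.3: "Case report forms are to be completed on an ongoing basis". Section 8.4: "Corrections made to electronic CRFs will be tracked by audit trail and require PI or delegate sign-off". An entry can thus be added or changed after the readings are known. The audit trail shows the change but sets no criterion for exclusion.
- *Monitoring (6.6).* The monitor checks CRFs against source documents, which sets no criterion either.
- *De-identification (8.1).* This hides who the participant is, not the readings.
- *Withdrawal (8.3).* A reason must be noted when a participant withdraws. No visible text asks for the same when a subject is excluded from analysis.

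**How large could the effect be?** The documents give no alpha, power, error SD, accuracy statistic, acceptance limit or expected number of exclusions. The figure of 32 is attributed to the ISO standard and cannot be reproduced, and this point does not dispute it. What follows is illustration only.

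Inputs: 32 subjects (section 7.3); 100 subjects (assumed; section 6.1 gives a ceiling of 250 for calibration and validation together); k = 1, 2 or 3 subjects removed (assumed); independent normal differences, one per subject (assumed).

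Method: simulate n differences, remove k subjects, and take ratio = mean SD after removal / mean SD before. The reduction is 1 − ratio.

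Worst case, largest absolute differences removed:

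| Start | Removed | Left | Ratio | Reduction in SD |
|---|---|---|---|---|
| 33 | 1 | 32 | 0.922 | 7.8% |
| 34 | 2 | 32 | 0.867 | 13.3% |
| 35 | 3 | 32 | 0.823 | 17.7% |
| 100 | 1 | 99 | 0.966 | about 3.5% |
| 100 | 2 | 98 | 0.939 | about 6% |
| 100 | 3 | 97 | 0.916 | about 8% |

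Milder case, subjects taken at random from the quarter with the largest absolute differences: from 32 (leaving 31, 30, 29) the ratios are 0.970, 0.936 and 0.899, reductions of about 3%, 6% and 10%. From 100 they are 0.991, 0.981 and 0.971, about 1%, 2% and 3%.

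Removal unrelated to the difference: from 32 the ratios are 0.9998, 0.9994 and 0.9991, a change of less than 0.1%. The loss of spread comes from selection on the difference, not from losing subjects.

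Removal from one tail only: from 32, the mean shifts by about 0.07, 0.12 and 0.18 SD for k = 1, 2 and 3, in either direction.

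**The case against.** The strongest objection is that the gap is judged on incomplete text. Section 7.1 is a bare heading, 7.2 is not visible, 7.3 is partly redacted, and the visible steps of 6.5.3 skip several numbers. Those steps would be a natural place for ambient conditions, device checks or repeat rules, and the ISO procedure could add more. This stands as a limit: a criterion elsewhere cannot be ruled out. It does not remove the point, because the exclusion list itself is visible and refers to no such criterion.

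A second objection is that a fault can be recognised without using the difference. Section 6.5.3 says: "The three measurements need to be taken in quick succession of each other, with approximately 3 seconds between each measurement". An erratic set of three from one instrument is evidence in its own right. That is correct. It is why the rule only permits exclusion by size of error, and why the replacement wording must leave room for a within-instrument check.

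Third, the percentages say nothing about what will happen in this trial. The worst case needs exclusion strictly by rank of absolute difference. Section 6.1 also allows the validation to draw on other sponsor studies, which would dilute the effect of exclusions made here. Both points stand.

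Fourth, a sensitivity analysis that puts back readings with verified faults means little on its own, and the listing alone would give most of the transparency. This stands in part: the analysis is useful only when read beside the listed reasons.

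A reader might infer that the plan intends to discard inconvenient results, or that reference-thermometer faults cannot be recorded at all. The documents support neither. Nothing visible suggests intent, and the CRF may carry deficiencies of the comparator.

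**Conclusion.** The point holds as a cheap improvement. The two data-driven grounds in 7.4.1 require no evidence independent of the outcome and no masking, and no listing or retained-subject analysis is visible, so selection on the outcome is possible and would not be evident to a reader. The possible understatement of spread runs from negligible, if exclusions are unrelated to the difference, to about 8%, 13% and 18% for 1, 2 or 3 worst-case removals that leave 32 subjects. It is smaller with more subjects or with pooled data. These sizes rest on normal differences, one per subject, with the SD as a generic measure of spread; the accuracy statistic actually used is not visible. Confidence is medium because of the redacted text.

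**What to change.** Replace the two data-driven bullets in 7.4.1 with wording such as:

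> Any subject for whom a specific cause is established independently of the Rad-G-minus-reference difference: a device deficiency recorded for the Rad-G or the reference thermometer; a failed functional check of either instrument; an instrument error flag or corrupted file; an interfering condition noted on the CRF at the time of measurement; or failure of a within-instrument plausibility or repeatability rule that is set before the validation data are examined and applied to each instrument's readings separately. The decision is made without sight of the difference and before the validation comparison.

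Then add:

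> Every exclusion is listed with its reason. The accuracy analysis is repeated, as a sensitivity analysis read beside that list, with subjects excluded under this bullet who completed at least one full round and have usable readings put back.

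If a criterion already exists in text that is not public, 7.4.1 should cross-refer to it. The antipyretic and incomplete-round grounds stay as they are, and the main analysis stays primary.

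The cost is a wording change, one listing, one extra table, and an exclusion review that hides the difference, for example by reviewing each instrument's data separately. The accuracy figures may come out slightly less favourable.
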